3.2 Exclusion Criteria

A patient will be excluded from this study if she meets any of the following criteria:

- 3.2.1 Participants who have a history of allergic reactions attributed to compounds of similar chemical or biologic composition to neratinib or fulvestrant.
- 3.2.2 Participants who have known hypersensitivity to any component of loperamide or colestipol.
- 3.2.3 Participants who have received previous therapy with neratinib.

- 3.2.4 Participants who have received anti-cancer therapy (including chemotherapy, biological therapy, investigational agents, hormonal therapy, or other anti-cancer therapy) or radiotherapy within ≤ 14 days prior to the planned initiation of investigational products, or those who have not recovered to grade ≤ 1 from adverse events due to their most recent therapy (excepting alopecia).
- 3.2.5 Participants who have had any major surgery ≤ 28 days prior to the planned initiation of study therapy, or those who have not recovered from adverse events due to agents/surgery administered more than 4 weeks earlier.
- 3.2.6 Participants who are receiving any other investigational agents.
- 3.2.7 Known brain metastases that are untreated, symptomatic, or require therapy to control symptoms. Participants with a history of treated central nervous system (CNS) metastases are eligible. Treated brain metastases are defined as those without ongoing requirement for corticosteroids, as ascertained by clinical examination and/or brain imaging (magnetic resonance imaging or CT scan) completed during screening. Any corticosteroid use for brain metastases must have been discontinued without the subsequent appearance of symptoms for ≥ 7 days prior to registration. Treatment for brain metastases may include whole brain radiotherapy, radiosurgery, surgery or a combination as deemed appropriate by the treating physician. Radiation therapy must be completed at least 14 days prior to registration, as specified in Section 3.2.4..
- 3.2.8 Participant has active, uncontrolled cardiac disease, including cardiomyopathy, congestive heart failure (New York Heart Association functional classification of ≥ 2), unstable angina, myocardial infarction within 12 months of enrollment, or ventricular arrhythmia.
- 3.2.9 Participant has a QTc interval >470 ms or known history of QTc prolongation or Torsade de Pointes. Note: correction may be made using any method of QTc calculation (i.e. QTcF)
- 3.2.10 Participant has an active infection or unexplained fever $>38.5^{\circ}\text{C}$ (101.3°F).
- 3.2.11 Participant has had another malignancy within the past 5 years with the exception of a) adequately treated basal cell carcinoma, squamous cell skin cancer, or thyroid cancer; b) carcinoma in situ of the breast, cervix or vulva; or c) cancer considered cured by surgical resection or unlikely to impact survival during the duration of the study, such as localized transitional cell carcinoma of the bladder, or benign tumors of the adrenal or pancreas.
- 3.2.12 Participant has significant chronic gastrointestinal disorder with diarrhea as a major symptom (e.g., Crohn's disease, malabsorption, or Grade ≥ 2 (NCI CTCAE v.4.0) diarrhea of any etiology at screening).

- 3.2.13 Participant has known active infection with hepatitis B or hepatitis C virus. Hepatitis B and C serology testing is not required, unless active infection is suspected.
- 3.2.14 Participant is unable or unwilling to swallow tablets.
- 3.2.15 Participant has evidence of significant medical illness, abnormal laboratory finding, or psychiatric illness/social situations that would, in the Investigator's judgment, limit compliance with study requirements.
- 3.2.16 Pregnant women are excluded from this study because fulvestrant is a SERD agent with the potential for teratogenic or abortifacient effects. Because there is an unknown but potential risk for adverse events in nursing infants secondary to treatment of the mother with neratinib and/or fulvestrant, breastfeeding should be discontinued if the mother is treated with neratinib and/or fulvestrant.

3.3 Inclusion of Women and Minorities

Women of all races and ethnic groups are eligible for this trial. Men are not eligible, as no data exist to our knowledge on the effect of fulvestrant in male breast cancer.

4. REGISTRATION PROCEDURES

4.1 General Guidelines for DF/HCC Institutions

Institutions will register eligible participants in the Clinical Trials Management System (CTMS) OnCore via the Office of Data Quality. Registrations must occur prior to the initiation of protocol therapy. Any participant not registered to the protocol before protocol therapy begins will be considered ineligible and registration will be denied.

An investigator will confirm eligibility criteria and a member of the study team will complete the protocol-specific eligibility checklist.

Following registration, participants may begin protocol therapy. Issues that would cause treatment delays should be discussed with the Overall Principal Investigator (PI). If a participant does not receive protocol therapy following registration, the participant's registration on the study must be canceled. Registration cancellations must be made in OnCore as soon as possible.

4.2 Registration Process for DF/HCC Institutions

DF/HCC Standard Operating Procedure for Human Subject Research Titled *Subject Protocol Registration* (SOP #: REGIST-101) must be followed.

4.3 General Guidelines for Other Investigative Sites

Eligible participants will be entered on study centrally at the Coordinating Center through the Study Coordinator or Project Manager. The list of required forms can be found in Section 4.4.

It is recommended that participants begin protocol treatment within 7 business days, and no more than 30 days from registration. Issues that would cause treatment delays should be discussed with the Overall PI. If a participant does not receive protocol therapy following registration, the participant's registration on the study must be canceled. The Study Coordinator should be notified of cancellations as soon as possible.

4.4 Registration Process for Other Investigative Sites

To register a participant, the following documents should be completed by the research nurse or data manager and faxed [REDACTED] or e-mailed [REDACTED] to the Project Manager:

- Signed participant consent form
- HIPAA authorization form
- Eligibility Checklist
- Baseline exam note including medical/surgical history, ECOG, vital signs
- EKG report
- MUGA or echocardiogram report
- Laboratory report including results for CBC, Chemistries, Urinalysis, and Urine Pregnancy Test
- Tumor Evaluation (MRI or CT and clinical assessment of visible of palpable lesions) Report
- Pathology Report and documentation of ER/PR and HER2 status
- Bone Scan Report (if done)
- Documentation of tissue availability (per eligibility criteria 3.1.8)

The Coordinating Center will review the submitted documents in order to verify eligibility and consent. To complete the registration process, the Coordinating Center will:

- Follow DF/HCC Standard Operating Procedure for Human Subject Research Titled *Subject Protocol Registration* (SOP #: REGIST-101) and register the participant on the protocol.
- Upon receiving confirmation of registration, the Coordinating Center will inform the Participating Institution and provide the study specific participant case number, and, if applicable, assigned treatment and/or dose level.

Treatment may not begin without confirmation from the Coordinating Center that the participant has been registered.

Randomization can only occur during normal business hours, Monday through Friday from 8:00 AM to 5:00 PM Eastern Standard Time.

5. TREATMENT PLAN

5.1 Treatment Regimen

Neratinib and fulvestrant will be administered in 4 week cycles, with 28 consecutive days defined as a treatment cycle. Treatment will be administered on an outpatient basis. There is no specific order of administration for neratinib and fulvestrant. Reported adverse events and potential risks are described in Section 7. Appropriate dose modifications are described in Section 6. No investigational or commercial agents or therapies other than those described below may be administered with the intent to treat the participant's malignancy.

Regimen Description					
Agent	Premedications; Precautions	Dose	Route	Schedule	Cycle Length
ARM A					
Neratinib	Loperamide and Colestipol (see Section 5.3.3)	240mg (six 40mg tablets)	Orally	Neratinib: once daily, continuous Loperamide: Days 1-28, continuous Colestipol: Days 1-28, continuous	28 days (4 weeks)
Fulvestrant		500mg (two injections of 250mg each)	Intramuscularly	Cycle 1: Day 1, 15 Cycle 2 and all subsequent cycles: Day 1	
ARM B					
Neratinib	Loperamide and Colestipol (see Section 5.3.3)	240mg (six 40mg tablets)	Orally	Neratinib: once daily, continuous Loperamide: Days 1-28, continuous Colestipol: Days 1-28, continuous	28 days (4 weeks)

5.2 Ovarian Suppression

Ovarian suppression with LHRH agonists (goserolin or leuprolide) per standard institutional or regional practices should be followed in pre-menopausal and peri-menopausal patients (i.e start on LHRH agonist at time of study treatment start). Postmenopausal patients are defined as no spontaneous menses over 12 consecutive months or post bilateral surgical oophorectomy.

5.3 Pre-Treatment Criteria

5.3.1 Cycle 1, Day 1

- Absolute neutrophil count $\geq 1,000/\mu\text{L}$
- Platelets $\geq 75,000/\mu\text{L}$
- Hemoglobin $\geq 8\text{g/dL}$
- Total bilirubin $\leq 1.5 \times$ upper limit of normal (ULN)
- AST(SGOT)/ALT(SGPT) $\leq 3 \times$ institutional ULN without liver metastases, or $\leq 5 \times$ institutional ULN with liver metastases
- Creatinine clearance $\geq 50 \text{ mL/min}$
- Left ventricular ejection fraction $\geq 50\%$, as determined by RVG (MUGA) or echocardiogram(ECHO) within 60 days prior to initiation of protocol therapy

5.3.2 Subsequent Cycles

- Absolute neutrophil count $\geq 1,000/\mu\text{L}$
- Platelets $\geq 75,000/\mu\text{L}$
- Hemoglobin $\geq 8\text{g/dL}$
- Total bilirubin $\leq 3 \times$ upper limit of normal (ULN)
- AST(SGOT)/ALT(SGPT) $\leq 5 \times$ institutional ULN without liver metastases, or $\leq 8 \times$ institutional ULN with liver metastases
- Creatinine clearance $\geq 50 \text{ mL/min}$

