6.1 Neratinib dose modifications

Neratinib dose delays and modifications should be made as indicated in the following table(s). Dose re-escalation is not allowed after a dose reduction.

If significant treatment-related toxicities have not recovered to Grade ≤ 1 or baseline grade, the patient may skip up to 28 days from the last scheduled dose. Patients should be re-evaluated weekly during the delay whenever possible. In patients randomized to the fulvestrant arm (Arm A), fulvestrant dosing can continue while neratinib is held or if neratinib is discontinued, as long as the toxicity is felt to be unrelated to fulvestrant. Cycles will not be delayed in the event neratinib is held, but will resume as originally scheduled. The missed dose(s) will not be made up.

Dosing may also be suspended for up to 28 days for unanticipated intercurrent medical events that are not associated with study treatment toxicity or disease progression.

Dose Reduction Table

Dose Reduction Level	Neratinib Dose
Starting Dose	240mg, daily
Dose level -1	160mg, daily
Dose level -2	120mg, daily

If a patient develops a toxicity requiring a dose reduction below Dose level -2 (120mg), neratinib should be permanently discontinued.

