6.1.4 Liver Toxicity

Guidelines for adjustment of neratinib in the event of liver toxicity are shown in Table 4.

Abnormal values in ALT concurrent with abnormal elevations in total bilirubin that meet the criteria outlined below in the absence of other causes of liver injury are considered potential cases of drug-induced liver injury (potential Hy’s Law cases) and should always be considered important medical events.

Patients who experience Grade \geq 3 diarrhea requiring IV fluid treatment or any signs or symptoms of hepatotoxicity such as worsening of fatigue, nausea, vomiting, right upper quadrant pain or tenderness, fever, rash or eosinophilia should be evaluated for changes

in liver function tests. Bilirubin and prothrombin time must also be collected during hepatotoxicity evaluation.

Table 4: Liver Function Test Abnormalities Requiring Dose Adjustment of Neratinib

NCI CTCAE V4.0	Action

Grade 2 AST/ALT (>3.0 - 5.0 x ULN)
 
OR
 
Grade 2 bilirubin (>1.5 - 3.0 x ULN)
	
 • Continue neratinib at same dose.

Grade 3 AST/ALT (>5 – 20x ULN)
 
OR
 
Grade 3 bilirubin (>3-10x ULN)
	
 • For participants with AST/ALT <grade 1 at baseline, resume neratinib at one dose level lower if recovery to baseline occurs within 21 days. • If grade 3 AST, ALT or bilirubin recurs despite one dose reduction, resume neratinib at a further dose reduction if recovery to baseline occurs within 21 days. • If grade 3 AST/ALT or bilirubin occurs despite this second dose reduction, permanently discontinue neratinib. Report as SAE. • Evaluate alternative causes.

Grade 4 AST/ALT (>20x ULN)
 
OR
 
Grade 4 Bilirubin (>10x ULN)
	
 • Permanently discontinue neratinib. • Evaluate alternative causes.

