
ALT > 3x ULN
 
AND
 
Total bilirubin > 2x ULN
 
AND
 
Alkaline phosphatase < 2x ULN
 
(potential Hy's law indicators of drug-induced liver damage)
	
 • Hold neratinib. The patient should return to the investigational site and be evaluated as soon as possible, preferably within 48 hours from awareness of the abnormal results. This evaluation should include laboratory tests, detailed history and physical assessment. Laboratory assessment must include: repeat AST and ALT, albumin, total bilirubin, direct bilirubin, PT, PTT and alkaline phosphatase. A detailed history, including relevant information, such as review of ethanol, concomitant medications, recreational drug and supplement consumption, family history, sexual history, travel history, history of contact with a jaundiced patient, surgery, blood transfusion, history of liver or allergic

NCI CTCAE V4.0	Action
	
disease, and work exposure, should be collected. Further testing for acute hepatitis A, B, or C infection and liver imaging (e.g., biliary tract) may be warranted. All cases confirmed on repeat testing as meeting the criteria mentioned above (i.e., ALT > 3 x ULN associated with bilirubin >2 x ULN and alkaline phosphatase <2 x ULN), with no other cause for liver function test abnormalities identified at the time should be considered potential Hy's Law cases, irrespective of availability of all the results of the investigations performed to determine etiology of the abnormal liver function tests.
 
 •Contact [REDACTED] immediately to discuss next steps, including evaluation of alternative causes, and management of investigational product(s). •These events must be reported as SAEs.

NOTE: During evaluation of hepatotoxicity, bilirubin must be fractionated, prothrombin time must be measured, and liver imaging should be considered.

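### Section 5.3.2 lets a cycle start at AST/ALT levels that Table 4 treats as Grade 3 in participants with liver metastases, and Table 4 gives no specific first-event Grade 3 instruction when baseline AST/ALT is raised

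*Combined protocol and SAP*

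**What the plan says.** **Cycle-start limits.** Section 5.3.2 sets the laboratory conditions for each cycle after the first. For liver enzymes, AST/ALT may be up to 5 x "institutional ULN without liver metastases, or $\leq 8 \times$ institutional ULN with liver metastases". Bilirubin may be up to 3 x ULN.

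**Dose modification.** Section 6.1.1 sends hepatic toxicity to Table 4 in Section 6.1.4, not to the general Table 1. Table 4 keeps the dose unchanged in the Grade 2 row, which ends at 5 x ULN for AST/ALT and 3 x ULN for bilirubin. The next row begins "Grade 3 AST/ALT (>5 – 20x ULN") and makes no distinction by liver metastases. It lists four actions:

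- First event: "For participants with AST/ALT <grade 1 at baseline, resume neratinib at one dose level lower if recovery to baseline occurs within 21 days".
- Recurrence despite one reduction: a further reduction, again subject to recovery to baseline within 21 days.
- Occurrence despite a second reduction: permanent discontinuation and an SAE report.
- Look for other causes.

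A separate row orders a hold when ALT exceeds 3 x ULN, total bilirubin exceeds 2 x ULN and alkaline phosphatase is below 2 x ULN. The table labels these as potential Hy's "law indicators of drug-induced liver damage".

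**Who can enter.** Section 3.1.7 admits AST/ALT up to 3 x ULN, or up to 5 x ULN with liver metastases.

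**General provisions.** For significant treatment-related toxicity that has not settled to Grade 1 or to the baseline grade, Section 6.1 says "the patient may skip up to 28 days from the last scheduled dose". The opening of Section 6 also permits further holds and reductions at the treating physician's discretion.

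**The concern.** The study calendar (Section 10, Table 7) schedules serum chemistries on Day 1 of each cycle. The same AST/ALT result is therefore read against Section 5.3.2 and against Table 4 on the same day. If the two disagree, one site can dose and another can withhold, and each can point to protocol text.

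The first-event restriction raises a separate problem. A participant who entered with raised enzymes, as Section 3.1.7 allows, may later reach Grade 3 and find that the only first-event action excludes her. Sites would then decide case by case whether to reduce the dose and what counts as recovery.

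What is at stake is consistent handling of a liver-safety signal across sites, and to a lesser degree comparable neratinib exposure between arms. Section 7.1.1.3 reports raised hepatic enzymes in more than 15% of fulvestrant patients, and only Arm A receives fulvestrant.

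**Working it through.** No sample size, power or alpha figure is involved. The check sets the thresholds side by side, in multiples of ULN.

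| Quantity | Section 5.3.2 allows | Table 4 Grade 2 (dose unchanged) | Table 4 Grade 3 | Overlap of 5.3.2 with Grade 3 |
|---|---|---|---|---|
| AST/ALT, no liver metastases | up to 5 | >3 to 5 | >5 to 20 | none |
| AST/ALT, liver metastases | up to 8 | >3 to 5 | >5 to 20 | >5 to 8 |
| Bilirubin, all | up to 3 | >1.5 to 3 | >3 to 10 | none |

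Without liver metastases, the cycle-start limits coincide with the top of Grade 2. The overlap comes entirely from the separate limit for liver metastases, which Table 4 does not mirror.

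**Step 1: where the overlap is a contradiction.** Take, for illustration, a participant with liver metastases, normal baseline AST, a Day 1 AST of 6 x ULN, normal bilirubin and no earlier event.

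- Section 5.3.2: 6 ≤ 8, so the cycle may start.
- Table 4: 6 > 5, so Grade 3. Neratinib may restart only after return to baseline within 21 days, one level lower. The row does not use the word hold, but a restart conditional on recovery implies one, and the reduction is explicit.

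Both cannot be followed by dosing neratinib that day.

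**Step 2: who has no first-event action.** Table 4 does not print its Grade 1 band. I take it as above ULN and up to 3 x ULN, directly below the printed Grade 2 band. The entry limits then admit baselines up to Grade 1 (3 x ULN, no liver metastases) or Grade 2 (5 x ULN, liver metastases). For such a participant at a first Grade 3 event:

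- action 1 is restricted to baseline AST/ALT below grade 1 and does not apply;
- action 2 presupposes one reduction and action 3 presupposes two;
- action 4 says nothing about dosing.

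The restriction is worded on AST/ALT, yet the row also covers Grade 3 bilirubin. A first Grade 3 bilirubin event in the same participants is therefore also without a specific instruction.

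**Step 3: whether another passage closes the gap.** Table 1 does not, because Section 6.1.1 directs hepatic toxicity to Table 4. Table 1 carries a footnote aligning its Grade 2 holds with the pre-treatment criteria for neutrophils, anemia and creatinine clearance. Table 4 has no such note for liver tests.

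**Step 4: a rough scale.** Table 5 gives Grade 3 rates on neratinib monotherapy of 1.1% for ALT and 0.5% for AST. Applied to the planned 152 participants, these give 0.011 x 152 ≈ 1.7 and 0.005 x 152 ≈ 0.8. This is only an order of magnitude. The rates are for monotherapy and an earlier CTCAE version, while this trial adds fulvestrant in one arm and admits raised baselines. The documents do not give the share of participants with liver metastases or raised baseline enzymes.

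**The case against.** The best defence is that cycle-start criteria and dose modification do different jobs, and that Section 5 refers dose changes to Section 6, so Table 4 simply prevails. Section 6.1 adds that cycles keep their schedule while neratinib is held. On that reading, the 8 x ULN limit could let fulvestrant go ahead in Arm A while neratinib waits. The reading is possible, but no passage states it. In Arm B neratinib is the only study agent, so for participants below grade 1 at baseline the allowance would then open a cycle with nothing to give. If the allowance is meant for participants with raised baselines, Table 4 has no matching first-event rule for them. Section 6 does call its instructions guidelines, but its discretion clause adds holds and reductions and does not choose between two limits.

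Several stronger readings are tempting, and the documents do not support them:

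- **Every participant with liver metastases faces a contradiction.** Only those below grade 1 at baseline do. The others fall in the gap, and counting them in both places would be wrong.
- **Raised-baseline participants have no Grade 3 rule at all.** The recurrence and discontinuation actions carry no baseline restriction, the combined row's hold applies at any baseline, and the Section 6.1 skip and physician discretion remain. What is missing is a specific first-event instruction.
- **The combined ALT/bilirubin row is a second contradiction.** ALT above 3 and up to 5 x ULN (8 with liver metastases) with bilirubin above 2 and up to 3 x ULN does pass Section 5.3.2. But the row is an explicit and more specific hold that a site can obey alongside the single-analyte limits. Table 4's own Grade 2 row overlaps it in the same way. A cross-reference is enough.
- **The 21 days in Table 4 conflict with the 28 days in Section 6.1.** The 28 days are a permissive general maximum, and the liver rule sits inside it, as do the shorter resumption windows for diarrhea in Table 2.

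Table 4 was read by program from a PDF. No gap is visible in the Grade 3 row, but a lost line cannot be fully excluded.

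**Conclusion.** The point holds in two parts:

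1. For participants with liver metastases and baseline AST/ALT below grade 1, a Day 1 value above 5 and up to 8 x ULN is accepted by Section 5.3.2 and is a Grade 3 event requiring recovery and a lower dose under Table 4.
2. For participants whose baseline AST/ALT is grade 1 or higher, Table 4 gives no specific instruction for a first Grade 3 event, although Section 3.1.7 admits them.

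This is an inconsistency and an omission in the text. It rests on taking Grade 1 as above ULN and up to 3 x ULN, and on reading the restart condition as implying a hold. The number affected may be small and cannot be derived from the documents. A reader might infer damage to the primary comparison, but nothing shows it: PFS is analysed by randomized arm, and the event target, power and alpha do not depend on these rules. It should be corrected because the instructions concern liver safety and are applied at several sites.

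**What to change.** Amend the text so that Section 5.3.2 and Table 4 can both be followed for the same Day 1 result:

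- Reconcile the cycle-start AST/ALT limit for liver metastases with the Grade 3 row.
- State which section governs when both apply, and whether the Section 5.3.2 limits concern neratinib, fulvestrant or both.
- Add a cross-reference making clear that the combined ALT/bilirubin row applies even when the Section 5.3.2 limits are met, as the present text already implies.
- State what applies to a first Grade 3 AST/ALT or bilirubin event when baseline AST/ALT is grade 1 or higher, and write out in the Grade 3 row the hold that is now only implied.

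The clinical values and actions are for the sponsor to choose. The cost is protocol amendment text and the usual notice to sites. No extra procedures, participants or analyses are needed.
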